The study subjects were male and female adults, enrolled at the Physical Therapy Department of the Physical Medicine and Rehabilitation Hospital in Kuwait City. Participants were included if they fulfilled the following criteria: 1) diagnosed of plantar heel pain in accordance with the Clinical Guidelines linked to the International Classification of Function, Disability and Health from the Orthopedic Section of the American Physical Therapy Association;²³⁸⁹ 2) aged 21 to 60 years at admission to the study, according to the Kuwaiti Ethical Committee; 3) a history of PHP for over one month, showing no improvements with previous conservative treatment; 4) the ability to walk 50 meters without any support; 5) the presence of MTrPs on plantar and calf muscles based on an initial physical examination carried out by a physiotherapist (MA) with experience and training in MTrPs; 6) accepting treatment from a male physiotherapist; 7) the ability to understand the study and the informed consent, as well as having signed the consent form.

The exclusion criteria were: 1) needle phobia; 2) needle allergy or hypersensitivity to metals; 3) the presence of coagulopathy or use of anticoagulants according to medical criteria; 4) the presence of peripheral arterial vascular disease; 5) pregnancy; 6) dermatological disease affecting the dry needling area; 7) the presence of any chronic medical condition which might preclude participation in the study, such as: malignancy, systemic inflammatory disorders (e.g., rheumatoid arthritis, psoriatic arthritis, ankylosing spondylitis, septic arthritis), neurological diseases, polyneuropathy, mononeuropathy, and sciatica; 8) treatment of plantar heel pain with needling or acupuncture during the last four weeks; 9) history of injection therapy in the heel over the previous three months; and 10) previous history of foot surgery or fracture. Receiving or implementing any form of treatment for the plantar heel pain (taping, night splints, massage therapy or footwear modifications) during the trial was considered withdrawal criteria.

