The sample-size calculation initially estimated that 39 participants per group would provide 80% power to detect a minimally important difference of 13 points in the pain domain of the Foot Health Status Questionnaire with a standard deviation of 20 points²⁰ and an alpha risk at 0.05. Allowing for a 20% loss to follow-up, a minimum of 47 participants was required in each group, equaling 94 participants in total. Based on initial data collection, the drop-out rate was recalculated to be 25% and the sample size was therefore increased to a total of 102 patients.

Patient and public involvement

No patients were involved in the design, recruitment or conduction of this study and the burden of the intervention was not assessed by patients themselves neither.

Randomization

Participants who fulfilled the inclusion criteria received standardized oral and written information, and, after consenting to participate in the trial, they were randomized using block randomization by blocks of 10 patients. Allocation was randomly assigned using a computer program (Randomizer, https://www.randomizer.org/) with random patient file number sequences generated by a third person not involved in the study.

Procedure and interventions

Two study groups were randomly formed. The first was treated with dry needling whereas the second group was treated with percutaneous needle electrolysis. In both groups, during the first session, all participants were taught a self-stretching protocol¹¹ which has been demonstrated to be effective for the management of PHP,²⁶¹¹ consisting of self-stretching of the calf muscles and

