Specific needles for dry needling were used during invasive treatments (Agu-punt, Spain). Needle length was determined by the location of the MTrP and ranged from 30 to 75mm in length (or longer if necessary, according to the patients' characteristics). The diameter of the needle was 0.25-0.30 mm. If the participant was sensitive to the needle insertion, the level of manipulation was reduced. If this measure proved insufficient for reducing the painful stimulus, needle manipulation ceased altogether and the needle was left in situ.^{21 22}

To maintain appropriate hygienic conditions during the invasive treatments, the clinician wore latex gloves and thoroughly cleaned the skin of the area to be needled with an antiseptic solution (70% Propan-2-ol, Skin-des). Upon removal of the needle, the area was firmly compressed for 10 seconds. The needle was discarded after each single use. In both groups, the intervention was terminated in the case of severe adverse effects and if the participant did not wish to continue.

Dry Needling Arm

Once the clinician located the MTrP, the needle was inserted over the same and a rapid needle entry was performed. The chosen technique for manipulating the needle was the technique described by Hong, which consists of a rapid needle entry and exit (fast in/fast out), in order to obtain a local twitch response, lasting 5 seconds employing a rhythmic movement at approximately 1Hz/sec (5 entries).

Percutaneous Needle Electrolysis Arm

The electrotherapy equipment used (Physio Invasiva, PRIM Fisioterapia, Spain) produced a

continuous galvanic current through the cathode while the patient held a hand-held anode. ¹⁸ Once the needle reached the relevant treatment area, this was needled in exactly the same manner as in the dry needling group, with the only difference being that the needle was transmitting an electrical current with an intensity of 1.5 mA (intensity was adapted to patient's characteristics according to their pain tolerance).

Study Variables

An independent assessor (MA) blinded to treatment group allocation conducted all assessments at baseline, and at the 4, 8, 12, 26 and 52-week follow-up. Demographic and disease data were collected at baseline.

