The primary outcome was the Foot Pain domain of the Foot Health Status Questionnaire (FHSQ), a validated measure of foot-health status²³ that has been used in similar trials, which evaluated the effectiveness of different interventions for plantar heel pain. ⁸ ²⁴ ²⁵ Individual item scores were inserted into a computer program (FHSQ V.1.03) which, after data transformation, provides a score ranging from 0 to 100 for each domain, ²⁶ with greater scores reflecting a better condition. ²⁷ Secondary outcomes were the Foot Function, Footwear and General Foot Health domains of the Foot Health Status Questionnaire, as well as the average and maximum level of pain over the past 48 hours using the visual analogue scale (VAS). Participants were explained that a score of 0 indicated the absence of pain whereas a score of 10 represented the maximum tolerable pain. Additionally, before each treatment session, they were asked to complete the VAS and after each treatment session, participants were asked to score their current pain immediately upon standing up and walking a few steps. The VAS is widely used and is both valid and reliable. ²⁸⁻³⁰

Quality of Life (QoL) was assessed with the EQ-5D-5L, which was completed by the participants at baseline and at the 4, 8, 12, 26 and 52-week assessments. The EQ-5D-5L self-report questionnaire is a descriptive system with five questions, each representing one dimension of Health-related Quality of Life, i.e. mobility, self-care, daily activities, pain/discomfort and depression/anxiety. Each dimension can be rated on five levels: no problems, slight problems, moderate problems, severe problems and extreme problems. Together, the results serve to classify people into 1 of 3125 possible health states.³¹ These health states are subsequently transformed to quality of life values with the EQ-5D-5L crosswalk value sets.³²

Statistical Analysis

The statistical analysis was performed using IBM SPSS Statistics (version 25, IBM, Chicago, IL) by intention to treat, with the last observation carried forward. The investigator who performed the analyses was masked to group allocation. The significance level for all statistical tests was set at $P \le 0.05$.

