Chi-squared tests were used to analyse if there were differences in categorical variables between groups at baseline. In addition, independent Student's t-tests and Mann-Whitney U tests were used for parametric and nonparametric quantitative variables, respectively. Chi-squared tests were used to evaluate the compliance of the self-stretching protocol.

Following recommendations to estimate treatment effects in RCTs, linear mixed models adjusted for baseline values were used to test the mean effect of treatment interventions at the follow up at the 4, 8, 12, 26 and 52-week follow-up, for the Foot Health Status Questionnaire and EQ-5D-5L measures. Linear mixed models adjusted for baseline values were used to test the mean effect of treatment interventions at the second session, third session, fourth session, and at the 4, 8, 12, 26

and 52-week follow-ups, for measures of VAS (average and maximum). Individual repeated measures (RM) ANOVAs were used to test time effects within each treatment group for primary and secondary outcomes. Cross-sectionally, at all linear mixed models and RM-ANOVAs, the Bonferroni correction was used to test between-group time point differences or within-group time changes, respectively. The Greenhouse-Geisser correction was applied for correcting against violations of sphericity, whereas eta-squared (η^2) was used to estimate the magnitude of the difference between both groups (0.01 small effect, 0.06 medium effect and 0.14 large effect).³³ Independent t-tests were used to determine any difference between groups for measures of level of pain immediately after each treatment session.

REFERENCES

- 1. Landorf KB. Plantar heel pain and plantar fasciitis. BMJ Clin Evid 2015;2015:1111.

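### Last observation carried forward is the only missing-data rule for the FHSQ Foot Pain analysis, and it can bias the between-group difference, usually most at week 52

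*Combined protocol and SAP*

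**What the plan says.** The opening paragraph of Statistical Analysis states that the analysis was done "by intention to treat, with the last observation carried forward". The sentence covers the analysis as a whole.

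The section then specifies, for the FHSQ and EQ-5D-5L, that "linear mixed models adjusted for baseline values were used to test the mean effect of treatment interventions" at each follow-up, with similar models for the VAS. It adds: "Individual repeated measures (RM) ANOVAs were used to test time effects within each treatment group for primary and secondary outcomes". Neither analysis is exempted from the carry-forward rule. Nothing says that the mixed models use observed data only. That the rule reaches these models is therefore a reading of the general sentence; the model paragraph does not repeat it. No missing-data assumption, multiple imputation or sensitivity analysis is given.

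Three other places bear on how much is missing, and why:

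- **Sample size (end of Participants).** The first allowance was 20% loss, then: "Based on initial data collection, the drop-out rate was recalculated to be 25" per cent, with the total raised to 102.
- **Study Variables.** The assessor "conducted all assessments at baseline, and at the 4, 8, 12, 26 and 52-week follow-up". No visit is named as primary.
- **Reasons for stopping.** Under the heading for the two invasive groups, "the intervention was terminated in the case of severe adverse effects and if the participant did not wish to continue", in both groups. The electrolysis arm is described with "the only difference being that the needle was transmitting an electrical current". In Participants, other heel-pain treatment (the list ends "massage therapy or footwear modifications) during the trial was considered withdrawal criteria") leads to withdrawal. Neither place says that score collection stops.

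**The concern.** Carrying forward fixes each missing score at its last value. For anyone lost before week 4, that value is baseline. Treatment is four weekly sessions, so a score used at week 52 may be almost a year old.

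For the comparison between arms, the trial's stated aim, this does no harm if both arms follow the same course and lose patients in the same pattern. It biases the difference in two situations:

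- drop-out differs by arm and scores would have changed after drop-out;
- the treatment difference itself changes over time.

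The error can go either way. A late-growing difference is diluted, a fading one is preserved artificially, and unequal loss can create a difference where none exists. Within-group change is distorted whenever mean scores move between visits, but that is secondary here.

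Unequal loss is not documented, but it is not excluded either. Only one arm receives current, and withdrawal for seeking other treatment could tie missing scores to poor response. The planned mixed model can use every observed visit under missing-at-random. Filling values in first gives up that advantage and treats imputed scores as observed.

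**Working it through.** **Inputs from the documents.** Difference 13, SD 20, alpha 0.05, 80% power, 39 per group, drop-out 20% then 25%, total 102, visits at weeks 4, 8, 12, 26 and 52.

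**The plan's own figures.** A two-sided two-sample t-test needs 38.14, so 39 per group. Then 39 × 1.20 = 46.8, so 47 per group and 94 in total. The revised total follows from the normal-approximation size of 38: 38/0.75 = 50.7, so 51 per group and 102. The calculations below use 51 per arm.

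**Assumptions, not in the documents.** Within-patient correlation 0.5, drop-out at random and permanent, and two timings for cumulative drop-out *d* by week 52:

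- Timing 1, constant weekly hazard: P(observed at week *w*) = (1 − *d*)^(*w*/52)
- Timing 2, equal hazard per visit interval: P(observed at visit *k*) = (1 − *d*)^(*k*/5)

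The expected carried-forward value at week 52 is the sum over visits of P(last observed there) × mean there. At *d* = 25%, P(last observed) is:

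| Week | 0 | 4 | 8 | 12 | 26 | 52 |
|---|---|---|---|---|---|---|
| Timing 1 | 0.0219 | 0.0214 | 0.0209 | 0.0697 | 0.1160 | 0.7500 |
| Timing 2 | 0.0559 | 0.0528 | 0.0498 | 0.0470 | 0.0444 | 0.7500 |

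About 2 (timing 1) or 6 (timing 2) of 102 have no post-baseline score. Ranges below run from timing 1 to timing 2.

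**Equal 25% drop-out**

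1. No true difference: no bias, type I error 5%.
2. Constant 13 from week 4: 13 × (1 − 0.0219) = 12.7 and 13 × (1 − 0.0559) = 12.3. Power 93% to 89%, against about 90% on observed data, so no material loss.
3. Growing 0, 3, 6, 10, 13:
   - Timing 1: 0.0209×3 + 0.0697×6 + 0.1160×10 + 0.75×13 = 11.4
   - Timing 2: 0.0498×3 + 0.0470×6 + 0.0444×10 + 0.75×13 = 10.6
   - Power about 86% to 76%, against about 90% on observed data.
   - With 20% to 30% drop-out the value spans 11.7 to 10.1.
   - Limiting scores to 0–100, with a mean rising to 60, gives 10.9 to 10.2 against a true 12.4. The relative dilution is unchanged at 12% to 18%.
4. Fading to a true 0 at week 52:
   - 10, 5, 3, 1, 0 reads +0.6 to +1.0
   - 10, 8, 6, 3, 0 reads +1.1 to +1.3
   - 10, 10, 10, 10, 0 reads 10 × (0.9781 − 0.75) = +2.3 to 10 × (0.9441 − 0.75) = +1.9

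**Unequal drop-out, no true difference.** Figures are the heavier-loss arm minus the other. The steepest course is 40-52-57-60-65-70 at weeks 0, 4, 8, 12, 26 and 52; the flattest is 40, then 60 throughout.

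| Drop-out | Flattest course | Steepest course | Type I error, flattest | Type I error, steepest |
|---|---|---|---|---|
| 20% v 30% | −0.2 to −0.5 | −1.1 to −1.7 | 5.2% to 5.4% | about 6% to 7–8% |
| 15% v 35% (extreme) | −0.4 to −1.0 | −2.2 to −3.3 | about 5% to 6% | about 9% to 14–15% |

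For example, on the steepest course with timing 2 the expected week-52 means are 66.86 (20% lost) and 65.19 (30% lost), a gap of −1.67. At week 4 the bias with 20% v 30% is only −0.1 to −0.5.

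**Within-group change, equal 25%.** A true 30-point gain reads 27.4 to 26.0; a true 20 reads 18.6 to 17.7.

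**Outer limits, all loss in one interval in both arms.** The growing case lies between 0.75×13 + 0.25×0 = 9.75 and 0.75×13 + 0.25×10 = 12.25. For 20% v 30% on the steepest course, the bias lies between −0.5 and −3.0.

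Power and type I error come from 6,000 simulated trials, using one baseline-adjusted week-52 test at 0.05. Maximum likelihood on all observed visits had bias below 0.05 points (without the 0–100 limit) and 91.4% power in the growing case.

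**Drop-out that also depends on the last observed score.** A separate simulation (correlation 0.6, both arms improving by 30 points, no true difference) gave −1.8 points and 7.4% type I error at about 22% v 32% drop-out, and −3.7 points and 17% at about 16% v 37%. The missing-at-random estimate stayed within 0.1 point of the truth.

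**The case against.** Nothing in the documents shows that the bias occurs. Drop-out is one pooled rate, the stopping rule applies to both groups, and scoring may have continued after withdrawal. The milder cases are mild: no bias with equal drop-out and no effect, no material loss with a constant effect, and at most 1.7 points for 20% v 30% under the two timings. All of this stands, and it limits the weight of the point.

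The error rates above ignore the Bonferroni correction that the plan applies to time-point comparisons. If that means five visits at 0.01 each (the family is not stated), type I error for 20% v 30% on the steepest course is about 1.6% to 1.7% against 1%. Power in the growing case is about 67% to 51%, against 71% to 74% in those observed at week 52. The absolute figures change; the relative inflation and loss remain.

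Week 52 is not always the worst visit. With a constant 13-point effect and 5% lost before week 4, the bias is −0.65 at every visit. With means flat after week 4 and all loss later, it is zero even at 15% v 35%. Hence usually, not always.

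The mixed model is also biased if missingness depends on unobserved scores. That is true, and it is why a missing-not-at-random analysis belongs in the fix.

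The separately published protocol was not available and may say more. The plan reviewed here still needs to state its own rule.

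**Conclusion.** The concern holds and should be fixed. That carrying forward is the only stated rule, and that it can bias the comparison, is certain. The size in this trial is unknown, because drop-out by arm and visit and the course of scores are not given.

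Under the assumed random drop-out and the two timings, the week-52 between-group bias runs from none to 2.4 points of dilution (13 − 10.6) with equal 25% loss and a growing effect, and up to 3.3 points with a deliberately extreme imbalance. That is small to moderate against 13 points. It can still cost power or raise the false-positive rate, and drop-out related to earlier scores can make it somewhat worse.

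**What to change.** Replace the carry-forward sentence with a paragraph that does the following:

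- **Primary estimate.** Take between-group effects on FHSQ, EQ-5D-5L and VAS from the planned mixed model (arm, visit, arm-by-visit, baseline), fitted to all observed visits under missing-at-random with nothing carried forward.
- **Scores after withdrawal.** State whether they were collected after withdrawal or after the intervention ended. If they exist, use them, in line with intention to treat, and say that the effect is then estimated regardless of other treatment.
- **Within-group change.** Estimate it from a mixed model on observed data in place of the RM-ANOVAs.
- **Reporting.** Give drop-out by arm, visit and reason, and the number in each arm with no post-baseline value.
- **Sensitivity.** Add multiple imputation with imputed FHSQ pain scores shifted by 0 to −13 points, in each arm alone and in both, and report where the conclusion changes. Keep carrying forward only as a further sensitivity analysis.

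The methods are written in the past tense. If carried-forward results already exist, report both analyses and label the observed-data one post hoc, to guard against selective choice.

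Cost: one paragraph, a refit of planned models, one substituted model and one sensitivity analysis, with no new data. Intervals widen slightly: the week-52 estimate had SD 3.9 against 3.6 to 3.7 in the equal-drop-out null simulation, and 3.9/3.7 to 3.9/3.6 is about 5% to 8% more.

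### Pain straight after each session is compared by t-tests without a covariate, although a VAS completed before session 1 could sharpen them; the gain depends on an unstated correlation

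*Combined protocol and SAP*

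**What the plan says.** Under Study Variables, the listed VAS outcomes are the "average and maximum level of pain over the past 48 hours using the visual analogue scale (VAS"), both secondary. Post-session pain is introduced afterwards as an extra measurement: "before each treatment session, they were asked to complete the VAS and after each treatment session, participants were asked to score their current pain". What is scored after the session is "current pain immediately upon standing up and walking a few steps". Procedure and interventions gives four weekly sessions, so there are four such scores per participant.

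Under Statistical Analysis, these scores are handled in one sentence: "Independent t-tests were used to determine any difference between groups for measures of level of pain immediately after each treatment session". It mentions no covariate. The same section treats the VAS average and maximum differently: "Linear mixed models adjusted for baseline values were used to test the mean effect of treatment interventions at the second session", and then at the later sessions and follow-ups. The FHSQ and EQ-5D-5L are also analysed by baseline-adjusted mixed models. A single threshold of P ≤ 0.05 applies to every test. The Bonferroni sentence covers the mixed models and the repeated-measures ANOVAs, and does not name these t-tests.

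**The concern.** The trial holds a pain score taken before any treatment, and the plan uses baseline adjustment for its other between-group VAS comparisons after treatment begins. Leaving the same kind of information out of the post-session comparisons can make them less precise than the data allow.

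The stake is limited. Post-session pain is neither the primary nor a listed secondary outcome, and the trial's main conclusion does not rest on it. The question is whether a short-term difference in pain between the needling techniques is estimated as sharply as it could be at almost no cost.

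**Working it through.** **Inputs.** The Participants section gives a total of 102, so 102/2 = 51 per arm if allocation is equal. Alpha is 0.05 (Statistical Analysis); sidedness is not stated and two-sided is assumed. There are four sessions. The documents give no SD for post-session pain and no correlation r between the pre-session-1 VAS and post-session pain, so effects are in SD units and r is shown over a range. The 0.5 SD difference is an assumption. The plan states no power or precision figure for this comparison, so there is none to reproduce.

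**Unadjusted t-test.** The 95% half-width is t(0.975; 100) × √(2/51) = 1.9840 × 0.1980 = 0.393 SD. Power for 0.5 SD, from the noncentral t with noncentrality 0.5 × √(51/2) = 2.525 and 100 df, is 70.6%.

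**ANCOVA with one covariate.** The residual variance is multiplied by (1 − r²). Estimating the slope costs a factor of about 1 + 1/(2 × 51 − 4) = 1 + 1/98, and one degree of freedom. The interval width relative to the t-test is therefore

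√[(1 − r²)(1 + 1/98)] × t(0.975; 99)/t(0.975; 100), where the last ratio is 1.9842/1.9840 = 1.0001.

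At r=0.3, for example: √(0.91 × 1.0102) × 1.0001 = 0.959. Power uses noncentrality 2.525/√[(1 − r²)(1 + 1/98)] and 99 df.

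| r | Width ratio | Change in width | Half-width (SD) | Power at 0.5 SD |
|---|---|---|---|---|
| t-test | 1 | none | 0.393 | 70.6% |
| 0 | 1.005 | 0.5% wider | 0.395 | 70.1% |
| 0.1 | 1.000 | unchanged | 0.393 | 70.5% |
| 0.2 | 0.985 | 1.5% narrower | 0.387 | 71.9% |
| 0.3 | 0.959 | 4.1% narrower | 0.377 | 74.1% |
| 0.5 | 0.871 | 12.9% narrower | 0.342 | 81.9% |
| 0.7 | 0.718 | 28.2% narrower | 0.282 | 93.6% |

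Break-even is where the ratio equals 1, at r of about 0.10.

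**If a mixed model were used and its Bonferroni rule applied.** With four sessions the per-session level is 0.05/4 = 0.0125. The same power formula at that level gives about 49.5%, 51.0%, 53.8% and 64.0% at r=0.1, 0.2, 0.3 and 0.5, all below the present 70.6%.

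**The case against.** The strongest reply is that this is an optional refinement. A t-test on an additional measure in a randomised trial is a sound analysis. That stands, and it is why the priority is low.

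A reader might infer that the plan breaks its own baseline-adjustment rule. The documents do not support that. The mixed models adjust each outcome for its own baseline, and no baseline rating of current pain on standing and walking is described. The pre-session VAS appears to be the 48-hour average and maximum, because those are the items modelled from the second session on. It is a related item, not the same one. For session 4 it was also taken about three weeks earlier, so r may be low and the gain nil. This also stands: the size of the loss cannot be fixed from the documents.

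A reader might also want all four tests recast as one mixed model, to match the rest of the plan. That would bring them under the plan's Bonferroni rule for all linear mixed models and, if the rule were applied, cost more power than the covariate returns at any r up to 0.5. This objection counts against that remedy. It does not count against adding a covariate to each session's comparison.

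Finally, the document is in the past tense. If the tests have been run, a prespecified change is no longer possible. That limits the fix to a disclosed supplementary analysis.

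**Conclusion.** The point holds as a minor matter of precision. A pre-treatment VAS that the trial already collects is left out of the four post-session comparisons. With 51 per arm, using it would at worst widen an interval by 0.5%, would break even at r of about 0.10, and would narrow it by 4.1% at r=0.3 and 12.9% at r=0.5. The loss is small at low correlations but would not be at r=0.7. These figures assume equal arms, complete data, a two-sided 5% level and the same r at every session.

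Two stronger readings should be resisted. The t-tests are not biased or invalid: randomisation protects them and each holds its 5% level. Nor can one say that published intervals are too wide, because the documents do not say that confidence intervals are reported for these tests. Multiplicity over the four tests is a separate matter that adjustment does not change; it is a reason to label the results exploratory.

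**What to change.** Keep one comparison per session and replace each t-test with an ANCOVA: a linear regression of post-session pain on arm, adjusted for one VAS item taken before session 1. Choose either the average or the maximum, name it before analysis, and use it for all four sessions. Do not adjust for the VAS taken before sessions 2 to 4, because those scores are post-randomisation and treatment may have changed them. Report the four adjusted differences with 95% confidence intervals, labelled exploratory.

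If a mixed model is preferred, state explicitly whether the plan's Bonferroni rule for all linear mixed models applies to it, since applying the rule would lower per-session power.

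If the t-tests have already been run, keep them and report the ANCOVA beside them as a disclosed post hoc analysis. Show it once with the average and once with the maximum as covariate, so that neither is selected after the fact.

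The cost is two or three sentences of analysis wording and no new data. The downside is the 0.5% wider interval if the covariate carries no information. Priority: low; the team could make this change, but nothing in the main analysis depends on it.
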